### **1.2.1 WAIT-LISTED PATIENTS ARE INCREASING IN NUMBER AND MEDICAL COMPLEXITY**

There are 3500 patients active on the waiting list in Canada, with over 800 deceased donor transplants performed annually.(11) In comparison, over 92,000 patients are currently wait listed in the United States with approximately 10,600 deceased donor transplants performed annually.(12) Wait-list candidates are increasingly complex. For example, the proportion of transplant candidates  $\geq 50$  years increased from 29% to 62% between 1991 and 2011,(12) while the percentage with type I or type II diabetes increased from 23% to 28% between 1998 and 2008.(13)

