### **1.2.2 LONGER WAITING TIMES AND CHANGING DONOR CHARACTERISTICS INCREASE CAD RISK**

Despite efforts to increase organ donation, the demand for transplantation continues to exceed the supply of transplantable organs. The median waiting time for deceased donor transplantation increased from 2.8 to 4.6 years between 2004 to 2006, and in 2011 the median waiting times for Canadian transplant recipients ranged from 864 to 1954 days (2.3-5.3 years) (Figure 1, Appendix).(14) Exposure to dialysis is a major factor increasing the risk of cardiac events before and after transplantation.(15) As a result, the cardiac

fitness of wait-listed patients for transplant surgery must be maintained for longer time periods. Due to the organ shortage, patients are now transplanted with kidneys from older deceased donors, and donation after circulatory death donors that have more peri-operative complications, and a higher risk of peri-operative cardiac events.(12)

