## **3.0 ELIGIBILITY CRITERIA**

Inclusion of incident wait-listed patients (i.e. patients activated to the waiting list after the start of the trial) and prevalent wait-list patients (i.e. patients already on the waiting list before the start of the trial) will enable successful enrolment, and ensure a high proportion of patients undergo transplantation during study follow-up. Only patients with an anticipated transplant date  $> 12$  months from the date of enrolment will be included. The time to transplantation of wait-list candidates can be estimated in each center based on ABO blood type, and immunology testing for anti-HLA antibodies. Enrolment in the pilot trial will be enriched to include at least 66% prevalent wait-listed patients so that

approximately 50% of patients are expected to undergo transplantation during the 24 month pilot trial follow up period.

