### **3.2 Exclusion criteria:**

- a) patients with signs or symptoms suggestive of active cardiac disease such as unstable coronary syndromes, decompensated heart failure, uncontrolled arrhythmia, new arrhythmia or conduction abnormality, valvular heart disease;
- b) patients who have been put “on hold” for transplantation due to a medical problem (e.g. an infection);
- c) prior extra-renal transplant recipients;
- d) multi-organ transplant candidates (e.g. kidney pancreas transplant candidates);
- e) patients with a planned living donor transplant;
- f) patients receiving dialysis in a non-local unit
- g) patients with a non-approved requirement for surveillance echocardiography

Table 3 Estimating time to transplantation from date of first wait-listing. To be completed by Site Investigator in Each Center

Blood Group	PRA 0%	PRA 1-29%	PRA 30-79%	PRA $\geq$ 80%
A				
B				
AB				
O				

Figure 1.

Group 1 patients would be screen annually, group 2 patients would be screened every 24 months, and group 3 patients would be screened every 36 months according to the 2005 NKF Guidelines. Timing of screening tests would be determined according the date of the last screening test recorded on the transplant center chart.

The Framingham CVD risk calculator can be found at

<https://www.cvdriskchecksecure.com/FraminghamRiskScore.aspx>

\* Patients with known CAD include those with clinical, EKG or other evidence of CAD, but excludes patients with angiographically proven evidence of CAD. Patients with angiographically proven CAD would be included in group 1.

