#### 4.0 PATIENT RECRUITMENT AND INFORMED CONSENT

We will enroll approximately 24 patients per month during the six month enrolment period for a total sample size of 144 patients. With 6 enrolling centres – this is equal to four patients per month X 6 months. The monthly enrolment rate is informed by the requirement to enroll approximately 70 patients per month in twenty-three centers for 36 months to complete the definitive 2500 patient trial.

We plan to consent 40% of the eligible patients approached to participate in the pilot trial. This 40% target in the pilot trial exceeds the estimated consent rate of 34% required to complete the definitive trial.

We also aim to have 50% of participants undergo transplantation within 24 months of the date of enrolment. This is important to demonstrate the risk of no-regular screening.

This will be achieved by enrolling both incident and prevalent wait-listed patients in the trial. To ensure this objective each site will enrol at least 66% prevalent wait-list patients (i.e. 16/24 patients at a given site should be prevalent patients). The data co-ordinating centre will not provide randomization if the site's enrolment of prevalent patients falls below 66% during the pilot study.

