## **7.0 TRIAL OUTCOME ASCERTAINMENT**

Standardized Case Report Forms will be used to assess all outcomes and study personnel will undergo formal orientation to these CRFs.

**Primary outcomes:** 1) Protocol adherence: We will define adherence by completion of the expected number of screening tests during follow up. For example, the expected number of screening tests in a diabetic patient who did not develop symptoms would be zero in the no-regular screening group, while the same patient would be expected to completed two annual screening tests if randomized to regular screening. Tests performed for clinical symptoms of CAD will be excluded from the determination of adherence.

Screening tests in patients randomized to the regular screening arm will be arranged by study personnel under direction of the site investigator. The study personnel will advise participants of their screening test and follow up directly with the testing facility to determine completion of the test and obtain test results. Use of cardiac screening tests and the reasons for testing, in both treatment groups will be determined using the following procedure: Patients will be interviewed in person during regular dialysis treatments or via telephone every six months. If an unscheduled test was performed the patient will be asked about the reason for test (i.e. presence of symptoms) and the identity of the organizing physician. We believe telephone interviews are feasible in this relatively healthy cohort of wait-listed patients. Patient interviews will be supplemented by review of the transplant center and dialysis patient chart or with treating physicians as necessary every six months. 2) Enrolment will be determined monthly from the Ottawa Hospital Research Institute (OHRI) which issues the randomization scheme.

3) Consent rate: Each transplant center maintains an up-to-date record of incident and prevalent active wait-listed patients. Eligibility criteria will be abstracted from the transplant center chart to a standardized case report form. The case report form will be completed by the study co-ordinator and will include the estimated time to transplantation as determined by the site investigator.

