For incident wait-list patients a monthly listing of newly activated wait-list candidates will be obtained from the transplant center during the enrolment period. Eligible incident patients will be sequentially approached with a target enrolment of up to 8 incident patients in each site. Willingness to enroll in the study will be recorded on each patient's case report form along with the reason for any refusal to consent. The number of incident patients approached to complete enrolment will be determined by review of the case report forms.

Prevalent Patients will be enrolled from the local dialysis population attached to each of pilot study transplant centers. The target number of prevalent patients at each site is 18 but there is no maximum number of prevalent patients that can be enrolled. Consent will be documented as described for incident patients.

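### Does the unexplained expectation that about half of participants will be transplanted within 24 months need correcting?

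*Combined protocol and SAP*

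**What the plan says.** Section 3.0 requires at least 66% prevalent patients and gives the reason: "approximately 50% of patients are expected to undergo transplantation during the 24 month pilot trial follow up period". Section 4.0 states 50% within 24 months as an aim, says it matters for showing the risk of leaving out regular screening, and adds: "To ensure this objective each site will enrol at least 66% prevalent wait-list patients". Sections 4.0 and 4.2 put this at 16 of 24 patients per site, and randomization is withheld from a site that falls below 66%. Section 7.0 goes further: "The target number of prevalent patients at each site is 18 but there is no maximum number of prevalent patients".

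Inclusion criterion (e) in section 3.1 admits only patients whose transplant is anticipated more than 12 months after enrolment. That date is estimated from blood group and panel reactive antibodies using Table 3, headed "Estimating time to transplantation from date of first wait-listing. To be completed by Site Investigator in Each Center". The table is a blank form. Section 7.0 says that the eligibility case report form "will include the estimated time to transplantation as determined by the site investigator".

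The background gives the only waiting-list figures. Section 1.2.2 reports a trend: "The median waiting time for deceased donor transplantation increased from 2.8 to 4.6 years between 2004 to 2006". Section 1.2.1 gives the size of the list and its yearly turnover: "There are 3500 patients active on the waiting list in Canada, with over 800 deceased donor transplants performed annually". For 2011, section 1.2.2 also gives a spread: "the median waiting times for Canadian transplant recipients ranged from 864 to 1954 days".

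**The concern.** A stated percentage with no calculation behind it invites a check, and two features make 50% look too high. Criterion (e) removes the patients nearest to transplantation, so a 24-month window works more like a 12-month one. In addition, most of the quoted waits run well beyond two years, so newly listed patients would seldom be transplanted in time and prevalent patients would have to supply nearly all the transplants.

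If the figure is too high, a reader expecting 0.50 × 144 = 72 transplants would see fewer. The pilot would then hold less peri-operative and post-transplant follow-up than section 4.0 wants, and a quota that blocks randomization would not deliver the result it is said to ensure.

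**Working it through.** **The plan's own figure.** It cannot be reproduced. The protocol gives no 24-month transplant probability for prevalent or incident patients, no time already waited and no pilot-centre waits. If incident patients contribute nothing, 50% overall needs 0.50/0.66 = 76% of prevalent patients transplanted within 24 months.

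**Inputs.** Waits of 864 days (2.366 years), 2.8 years, 4.6 years and 1954 days (5.350 years) from section 1.2.2, with 3 years added as an intermediate value; 800 transplants a year from a list of 3500 (section 1.2.1); prevalent share p of 2/3 (16/24) or 0.75 (18/24).

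**Fixed wait W.** Assume a steady list, prevalent patients spread evenly along it, and no deaths or removals. Criterion (e) leaves remaining waits between 1 and W years, so the prevalent share transplanted by 24 months is 1/(W − 1). For W above 2 years the incident share is 0. The total is p/(W − 1).

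**Varying waits, (e) applied as written.** Assume log-normal waits with median m and log-SD 0.2 to 0.6. Table 3 can give only a group estimate, so a patient who has waited a years is eligible if m − a exceeds 1. With S the probability of still waiting, the prevalent share is the integral of S(a) − S(a + 2) over a from 0 to m − 1, divided by the integral of S(a) over the same range. The incident share is 1 − S(2).

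| Wait | Fixed, p = 2/3 | Fixed, p = 0.75 | Log-normal, p = 2/3 |
|---|---|---|---|
| 864 days | 49% | 55% | 50-52% |
| 2.8 years | 37% | 42% | 37-42% |
| 3 years | 33% | 38% | 33-38% |
| 4.6 years | 19% | 21% | 18-22% |
| 1954 days | 15% | 17% | 15-18% |

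At two-thirds prevalent, the log-normal and fixed-wait results together correspond to about 70 to 75 of 144 patients at 864 days, 47 to 55 at 3 years, 26 to 32 at 4.6 years and 22 to 26 at 1954 days.

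**Break-even.** Under the fixed wait, 50% needs W = 1 + p/0.5. This is 2.33 years (852 days) at p = 2/3, 2.5 years (913 days) at p = 0.75, and 3 years (1096 days) if every participant is prevalent.

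**Other models.** If waits are exponential, time already waited carries no information and the share is 1 − 2^(−2/m): 44% at 864 days, 26% at 4.6 years and 23% at 1954 days. National turnover gives 1 − exp(−2 × 800/3500) = 37% on the same basis. With a fixed wait and (e) it gives 800/(3500 − 800) × 2/3 = 20%. The crude ratio 1600/3500 = 46% is not comparable, because it treats every participant as prevalent and ignores (e); at two-thirds prevalent it becomes 30%.

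**What depends on the 50%.** Section 2.2 derives 144 from the precision of an adherence of 90%: 1.96 × √(0.9 × 0.1/144) = 4.9 percentage points. The enrolment target of 24 a month and the consent target of 40% come from the needs of the definitive trial. Section 9.0 plans descriptive analyses only, with no comparison of clinical outcomes between groups at the end of the pilot. The transplanted share enters none of these.

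**The case for a change.** The strongest case for a change is that the wording goes beyond an aim: section 3.0 says expected, and section 4.0 says the quota is there to ensure the result. Every model above puts 50% only near the short end of the quoted waits. At 4.6 years or more, none exceeds 30% at two-thirds prevalent, even with (e) ignored. Deaths and removals, left out here, would lower the shares. Pilot patients enter the definitive analysis, and section 1.2.3 places the highest cardiac risk in the first month after transplantation, so fewer transplants mean less of the exposure that matters. The application for the definitive trial is planned after five months of enrolment, too early to have observed the true share. A basis could be given cheaply from estimates that sites already record.

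Most of this stands as description: the figure has no stated basis, and the quota raises the share without guaranteeing it. It does not show an error. National turnover and a between-centre range of medians cannot test a statement about six centres whose waits are not given, and the appendix figure cited for waiting times was not available for this check. The 66% is a floor and section 7.0 sets no ceiling, so the share can exceed the two-thirds column. A minimum of 16 and a target of 18 prevalent patients per site are compatible. The definitive trial's 2500 is not tied to a transplanted share anywhere in the protocol, and section 9.0 names only enrolment and consent analyses in support of the application.

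**Conclusion.** No change is needed. The 50% is an undocumented planning expectation, within reach where waits are near 864 days (about 49-52% at two-thirds prevalent, fixed or log-normal waits) and optimistic where they are long (15-18% at 1954 days). These shares rest on an assumed steady list, the assumed wait distributions, and no deaths or removals. Which end applies depends on the pilot centres' waits, which the protocol leaves each site to enter in Table 3.

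Restating the percentage or softening the claim that the quota ensures it would gain nothing in the pilot. Eligibility, quota, randomization check, sample size, all three feasibility outcomes and the descriptive analysis would stay as they are. A quota favouring patients who have already used up part of their wait is a sensible way to raise the transplanted share, whatever its value. Section 7.0 has transplant events collected by monthly contact with the centres, so the analysts will report the observed number and need no prior figure to interpret it.

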### **3.1 Inclusion criteria**

- a) Adult patients  $\geq$  18 years of age, able to provide informed consent
- b) Patients with dialysis-dependent renal failure and active on the deceased donor transplant waiting list.
- c) Patients expected to require further screening for CAD prior to transplantation by the current standard of care. Refer to Figure 1 below to determine screening frequency. It should be noted that some prevalent patients may already be past due for their cardiac screening test according to the current standard of care at the time of study enrolment. If randomized to the regular screening arm, these patients would be scheduled for a cardiac screening test within 1 month of enrolment.
- d) Investigator consented and signed off on patient eligibility.
- e) Patients anticipated to undergo transplantation more than 12 months from the date of enrolment. Although we cannot definitively predict the timing of transplantation, we will estimate this date based on ABO blood type, and immunology testing for anti-HLA antibodies indicated by panel reactive antibodies (PRA). The time to transplantation will vary between centers in each of these groups. Therefore the site investigator will complete Table 3 below to inform the time to transplantation in each center.

[figure not shown]
### **3.2 Exclusion criteria:**

- a) patients with signs or symptoms suggestive of active cardiac disease such as unstable coronary syndromes, decompensated heart failure, uncontrolled arrhythmia, new arrhythmia or conduction abnormality, valvular heart disease;
- b) patients who have been put “on hold” for transplantation due to a medical problem (e.g. an infection);
- c) prior extra-renal transplant recipients;
- d) multi-organ transplant candidates (e.g. kidney pancreas transplant candidates);
- e) patients with a planned living donor transplant;
- f) patients receiving dialysis in a non-local unit
- g) patients with a non-approved requirement for surveillance echocardiography

Table 3 Estimating time to transplantation from date of first wait-listing. To be completed by Site Investigator in Each Center

Blood Group	PRA 0%	PRA 1-29%	PRA 30-79%	PRA $\geq$ 80%
A				
B				
AB				
O				

Figure 1.

Group 1 patients would be screen annually, group 2 patients would be screened every 24 months, and group 3 patients would be screened every 36 months according to the 2005 NKF Guidelines. Timing of screening tests would be determined according the date of the last screening test recorded on the transplant center chart.

The Framingham CVD risk calculator can be found at

<https://www.cvdriskchecksecure.com/FraminghamRiskScore.aspx>

\* Patients with known CAD include those with clinical, EKG or other evidence of CAD, but excludes patients with angiographically proven evidence of CAD. Patients with angiographically proven CAD would be included in group 1.

#### 4.0 PATIENT RECRUITMENT AND INFORMED CONSENT

We will enroll approximately 24 patients per month during the six month enrolment period for a total sample size of 144 patients. With 6 enrolling centres – this is equal to four patients per month X 6 months. The monthly enrolment rate is informed by the requirement to enroll approximately 70 patients per month in twenty-three centers for 36 months to complete the definitive 2500 patient trial.

We plan to consent 40% of the eligible patients approached to participate in the pilot trial. This 40% target in the pilot trial exceeds the estimated consent rate of 34% required to complete the definitive trial.

We also aim to have 50% of participants undergo transplantation within 24 months of the date of enrolment. This is important to demonstrate the risk of no-regular screening.

This will be achieved by enrolling both incident and prevalent wait-listed patients in the trial. To ensure this objective each site will enrol at least 66% prevalent wait-list patients (i.e. 16/24 patients at a given site should be prevalent patients). The data co-ordinating centre will not provide randomization if the site's enrolment of prevalent patients falls below 66% during the pilot study.

#### **4.1 Incident patient identification and enrolment**

Although incident patients could be enrolled at the time of their initial transplant evaluation, patients usually require further evaluation and multi-disciplinary team discussion before they are officially activated to the list. Therefore the study co-ordinator should receive a listing of all newly activated wait-list patients on a weekly basis (i.e. on a Friday) from the Transplant Center to be approached the following week.

Patients who reside locally should be identified for potential participation first. Note this could include patients on peritoneal or hemodialysis in the home or in- center setting. An approach to contact and consent the patient for enrolment during a routine clinical encounter or dedicated study visit should then be defined (e.g. a telephone call followed by an in person enrolment visit during a dialysis treatment or outpatient clinic visit) using institution-specific policies and procedures.

The site PI should discuss eligible patients with the treating cardiologist (if applicable) to 1) confirm the cardiologist's agreement with participation in the trial 2) determine whether the patient meets any of the requirements for screening echocardiography (see Table 4 below). Patients declined for participation by their cardiologist will be considered ineligible.

#### **4.2 Prevalent patient identification and enrolment:**

At least 16/24 patients enrolled in each site will be prevalent patients.

In addition to meeting study inclusion/exclusion criteria, prevalent patients should be under chronic dialysis treatment in a location that is accessible to study co-ordinators (i.e. local patients).

The study co-ordinator should review all patients on the active transplant waiting list with the site PI, and identify eligible potential study participants who reside locally first.

The site PI should discuss eligible patients with the treating cardiologist (if applicable) to 1) confirm the cardiologist's agreement with participation in the trial 2) determine whether the patient meets any of the requirements for screening echocardiography (see Table 4 ). Patients declined for participation by their cardiologist will be considered ineligible.

**4.3 Informed Consent:** A study co-ordinator will approach eligible patients to obtain informed consent.

#### **4.4 Randomization**

A web-based randomization system will be used. A permuted blocked randomization method will be used to allocate patients. Patients will be stratified by centre and diabetic

status. A statistician, independent of the trial team, will generate the randomization scheme. The randomization process will consist of a computer-generated random listing of the treatment allocations stratified as above in variable permuted block sizes that will not be known to the investigators. The system will have backup in the form of a statistician and designated research assistant at the coordinating centre. Only the statistician and designated research assistant at the coordinating centre will have knowledge of the randomization codes. After confirming eligibility and obtaining informed consent, the study nurse will access the trial website and provide the subject's unique ID as well as a confirmation of consent and eligibility. The web site will provide the next available randomization number. The data co-ordinating centre will not provide randomization if the site's enrolment of prevalent patients falls below 66% during the pilot study.

